## Types of Sites

1. \* Select which of the following accurately describes this study

- Not Multicenter Study

---

 Multicenter Study - VCU Lead

---

 Multicenter Study - Non-VCU Lead

2. \* Select all sites where study interventions or interactions will occur and/or identifiable data will be held

---

 VCU Site

---

 Non-VCU Site (VCU Investigators are conducting/overseeing the conduct of the study)

3. \* Is there a community partner in this research study

 Yes No

ID: HM20011025

View: SF - VCU Site Details

## VCU Site Details

1. \* Select all VCU sites that will be utilized in this study

---

 Children's Hospital of Richmond at VCU

---

 Clinical Research Services Unit (CRSU)

---

 Massey Cancer Center

---

 VCU Health Community Memorial Hospital

---

 VCU Medical Center downtown

---

 VCU Monroe Park Campus

---

 VCU Qatar

---

 Other VCU Site

2. \* Provide details regarding each VCU Site including

- what clinics / facilities will be used

- resources that are available for the conduct of this study

Informed consent and collection of samples (extracted teeth) will occur at the Orthodontic Clinic at VCU School of Dentistry on the MCV campus.

Once the patient hands over the samples, water will be replaced with 0.1% Thymol solution (disinfectant). Samples in disinfectant will be stored in [name] laboratory in the School of Dentistry in a refrigerator until ready for analysis. The samples will be subject to micro CT, AFM at core facilities in the School of Engineering. These samples will not have any personal identifiers and people working with these samples will not know the source (patient information).

ID: HM20011025

View: SF - Study Funding

## Study Funding

1. \* Have you applied for funding

 Yes No

2. If so, is this study already funded

 Yes No

ID: HM20011025

View: SF - Funding Details

## Funding Details

1. \* Select all funding sources for this study (pending or awarded)

---

 Industry

---

 Direct Federal

---

 Non-Profit

---

 Indirect Federal

---

 State/Local Government

---

 Internal Grant

---

 Investigator/Departmental Funds

---

 None

---

 Other

2. Select all related proposals

There are no items to display

ID: HM20011025

View: SF - Study Population

## Study Population

**1. \* Provide the total number of individuals at VCU, and at other sites under the VCU IRB, that**

1. May participate in any study interaction or intervention (including screening, consenting, and study activities) AND/OR
2. You may obtain any data/specimens about (regardless of identifiability)

See the help text for additional guidance.

35

**2. If this is a multi-Center Project, what is the total anticipated number of subjects across all sites**

N/A

**3. \* Provide justification for the sample size**

With the number of patients seen in the VCU Orthodontic clinic, this is about the number that we expect to fit into our inclusion criteria. Assuming 80% power and a Wilcoxon rank-sum test, a sample size of 30 would be able to detect a significant difference in the two treatments if 70% of subjects have lower WSL scores on the tooth with Opal Seal (Reference: Noether, G.E. "Sample size determination for some common nonparametric statistics" Journal of the American Statistical Association 82(1987) pp. 645-647).

We are requesting increased recruitment of 35 to account for some attrition.

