## Research Description

1. \* Describe the study hypothesis and/or research questions. Use lay language whenever possible.

Primers are a type of 'glue' routinely used in orthodontics to attach brackets (metallic components) to the teeth. OpalSeal is a fluoride-releasing primer that has the potential to reduce cavities in patients receiving braces.

Orthodontic patients are at particular risk of developing two types of early carious lesions (decay):

- Around the brackets called White Spot Lesions and
- Along the sides of the teeth after slenderization procedure called inter-proximal reduction (IPR).

Our research questions are:

- Can OpalSeal offer protection against white spot lesions (WSL) around the brackets?
- Can OpalSeal offer protection against decay on the sides of teeth following IPR?

2. \* Describe the study's specific aims or goals. Use lay language whenever possible.

We know that fluoride is very effective in preventing dental decay (cavities) when applied in the form of a varnish on tooth surfaces.

The purpose of this study is to verify if fluoride-releasing primer (OpalSeal) offers more protection against early dental decay (cavity) compared to conventional primer (Transbond XT) during treatment with braces.

3. \* Describe the study's background and significance, including citations, or upload a citation list in document upload. Use lay language whenever possible.

Plaque is a sticky, colorless film of bacteria that constantly forms on our teeth that ferments sugars from diet to produce acids. These acids have been shown to dissolve enamel (outermost layer of tooth) that eventually forms a cavity. Having braces increases plaque build up and food accumulation around the brackets (1-2, 4-7), resulting in increased risk for dental decay (cavities).

The formation of white spot lesions (WSL) is a common risk in patients who undergo orthodontic treatment (1-4), especially those with poor oral hygiene practices (5). The prevalence ranges from 50-96%. WSL represent the early stages of caries (1,3,4) and can form within 4 weeks of the start of treatment (7). The lesions appear white, chalky, and opaque and can make the end result of orthodontic therapy very unaesthetic (3,6).

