See the help text for additional guidance.

Patients at the VCU Orthodontic clinic, 10 years and older, who have consented to for orthodontic treatment (braces) that involves extraction of at least 2 teeth (one on the right and the other on the left side of the mouth) will be approached for participation in the study. Interested participants will be recruited to the study following informed consent process. Dental extraction of teeth as part of orthodontic treatment is typically referred to an oral surgeon and it takes approximately three months to get this procedure. The standard clinical practice in the Department of Orthodontics is to begin treatment right away without waiting for extractions.

Since the teeth planned for extraction are on either side of the mouth, we will use a split-mouth design with random assignments for interventions (OpalSeal). Apart from the intervention, patients will be treated the same way they would be if they were not participating in research. All patients will be given oral hygiene instructions and they will have no additional appointments for research purposes.

Study related interventions will be restricted to teeth that are planned for extraction and will not involve other teeth. These interventions include:

1. Bonding brackets on to-be-extracted teeth, with one receiving OpalSeal
2. Selective grinding of enamel ( PR) on to-be-extracted teeth, with one tooth receiving OpalSeal
3. Collection of extracted teeth for laboratory analysis
4. Completion of a short survey

The patient will schedule the extraction appointment with the dentist of their choice (routine clinical protocol) and will update the Orthodontic clinic. Typically, the patients come to the clinic a day or two prior to extraction to get the wires removed (dentists will not extract the teeth with wires still on). At this time, the patient will be given labeled plastic jars containing water and will be instructed to collect the teeth after extractions. The corresponding dentist will be instructed to place the teeth in the jars and hand over the container to the patient. As is the regular protocol, patients will report to the Orthodontic clinic within a few days of extractions to have the wires replaced and continue treatment. Study personnel will collect the jars containing extracted teeth at this follow up appointment.

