All specimens will be transferred into 0.1% thymol solution (disinfectant) and stored until analysis. There will be no personally identifiable information on the jars. Samples will undergo the following tests:

- a. Scanning electron microscopy to analyze the surface topography
- b. Micro-CT to quantify the mineral density
- c. Atomic force microscopy to test surface roughness and hardness
- d. Fluorescence to quantify the residual amount of OpalSeal

The survey will help us understand how the patient controlled factors affect the incidence of WSL. For example, are right-handed patients more likely to develop WSL on the right side?

"The statistician will generate and provide a computer generated random assignment table to the resident [REDACTED]. The resident will be the only person that will be providing the interventions (OpalSeal or TransbondXT) to the study participants."

1. Bonding brackets on to-be-extracted teeth: Placing brackets on teeth are fundamental to moving teeth and teeth will have a bracket attached at the start of treatment. However, teeth planned for extractions do not receive any brackets in routine clinical practice. In our study though, we will place brackets even on to-be-extracted teeth until they are extracted. Since every patient will have at least two teeth that would be extracted, one of them would receive OpalSeal while the other will receive Transbond XT. The procedures for bonding will be consistent with clinical procedures and protocol for any orthodontic patient treated in the clinic.
2. Administering OpalSeal: OpalSeal will be applied to the teeth of interest following manufacturer's instructions for use (refer to the attached document).

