**See the help text for additional guidance.**

All signed informed consent documents and completed surveys will be stored in a locked cabinet in the PI's office. The extracted teeth will be collected in jars containing no PHI from the oral surgery clinic and will be stored in a refrigerator in locked laboratory (Dental Materials Laboratory, Wood Building 101) until analysis.

In our study, every patient will serve as his/her own control. This is because every patient will have two teeth extracted, one of which will receive OpalSeal and the other, Transbond XT. We will use a computer generated random number table to determine which tooth will receive OpalSeal or Transbond XT. We will generate a code based on:

- order of patient enrollment and
- whether the tooth received OpalSeal (e) or Transbond XT (c)
- date of tooth extraction

2. This key that links code to the patient will be stored in the PI's office computer that has restricted access (only to study personnel).

3. The key will be destroyed when the extracted teeth are collected from the patient. Since we would not be needing any PHI, this would decrease the risk of loss of confidentiality.

2. \* Who will have access to study data

PI, co-investigator, student researcher, and statistician will have access to the study data. They are all part of the study team.

3. \* If the study will code (i.e. de-identify) the research data by replacing subjects' names with assigned subject IDs, explain the following aspects of the coding process

1. The process for how subject IDs will be generated/assigned (e.g. random, sequential)

2. Whether there will be a key that links the subject ID with direct identifiers.

If a key will be created, describe

3. The place where the key will be stored

4. The role(s) of all individuals who will have access to the key

5. When the key will be destroyed

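### The 80% power at 30 patients is based on an independent-samples rank-sum test although the design is split-mouth, and no alpha or sidedness is stated

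*Protocol*

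**What the plan says.** The protocol's only power statement is in Study Population, item 3: "Assuming 80% power and a Wilcoxon rank-sum test, a sample size of 30 would be able to detect a significant difference", the condition being "if 70% of subjects have lower WSL scores on the tooth with Opal Seal". Recruitment is raised from 30 to 35 for attrition. The same paragraph also rests the number on feasibility: "this is about the number that we expect to fit into our inclusion criteria".

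The design is described in three places:

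- Research Description, item 4: "we will use a split-mouth design with random assignments for interventions (OpalSeal".
- The bracket-bonding step under the same item says of a patient's teeth to be extracted that "one of them would receive OpalSeal while the other will receive Transbond XT".
- Data Confidentiality and Storage, item 1: "In our study, every patient will serve as his/her own control".

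The aim (Research Description, item 2) is worded in one direction: whether OpalSeal "offers more protection against early dental decay (cavity) compared to conventional primer (Transbond XT". The protocol states neither a significance level nor whether the test is one-sided or two-sided.

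**The concern.** The rank-sum test treats the two sets of scores as independent samples. Here they are two teeth from the same mouth. The sizing paragraph is also inconsistent within itself. Its effect is a comparison of two teeth in one patient, whereas the rank-sum effect parameter is the probability that a randomly drawn tooth from one group scores lower than an independently drawn tooth from the other. A within-patient share has been put into a between-sample calculation.

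Without alpha and sidedness, a reader cannot tell what the 80% refers to. The paragraph also does not say whether the remaining 30% of patients score higher on the OpalSeal tooth or include ties, which matters a great deal for a test that uses only the direction of each difference.

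The paragraph names the rank-sum test for sizing only. If the same test were also applied to the paired scores, it would lose power as the two teeth of a patient became more alike.

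**Working it through.** **Inputs from the protocol:** power 80%; rank-sum test; 30; share 0.70 (Study Population, item 3); one tooth per treatment in each patient (Research Description, item 4). Item 1 of Study Population counts individuals, so 30 is read as patients, that is, 30 teeth per treatment.

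**Assumed, because not stated:** alpha 5%, two-sided; one-sided 5% is shown as the alternative.

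**1. The stated figure with the named test.** The standard large-sample rank-sum formula with equal groups is

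N = (z_alpha + z_beta)² / [12 · c(1 − c) · (p − 0.5)²], with c = 0.5 and p = 0.70.

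- Two-sided 5%: (1.960 + 0.842)² = 7.849, and 7.849 / (12 · 0.25 · 0.2²) = 7.849 / 0.12 = 65.4 teeth, or 33 per treatment. The stated 30 is not reproduced.
- Power at 30 per treatment (60 teeth): Phi(√(60 · 0.12) − 1.960) = Phi(√7.2 − 1.960) = 76.5%. Simulation with normal scores gives about 78%.
- If 30 were the total number of teeth: Phi(√3.6 − 1.960) = 47.5%.
- Share detectable with 80% power at 30 per treatment: 0.5 + √(7.849 / 180) = 70.9%.
- One-sided 5%: Phi(√7.2 − 1.645) = 85.0%, with 26 per treatment required. Then 30 suffices but is not the computed requirement.
- All 35 patients analysed, two-sided: Phi(√8.4 − 1.960) = 82.6%.

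**2. The paired counterpart.** Wilcoxon signed-rank test with exact critical values (328 at 30 pairs, two-sided). The differences are simulated as normal with 70% favouring OpalSeal, a standardised mean of 0.524.

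| Pairs | Two-sided 5% | One-sided 5% |
|---|---|---|
| 30 | about 77.6% | about 86% |
| 32 | 80.3% | 88% |
| 35 | about 84% | 90% |

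At 30 pairs, two-sided, 80% is reached at a share of about 70.6%. The shape of the differences matters more than this gap. With the share held at 70%, power is 61% for Laplace, 73% for logistic and 92% for uniform differences.

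**3. The sign test, which uses the 70% directly.** Exact test on untied pairs, 30 patients, 70% lower on OpalSeal, two-sided 5%:

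| Ties | Higher on OpalSeal | Power |
|---|---|---|
| 0% | 30% | 58.9% |
| 5% | 25% | 67.5% |
| 10% | 20% | 80.6% |
| 15% | 15% | 91.6% |
| 20% | 10% | 97.7% |

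One-sided 5% without ties: 73%.

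**4. The rank-sum test applied to paired scores.** Bivariate normal scores, within-patient share held at 70%, correlation assumed, two-sided 5%: power is 78% at correlation 0, about 70% at 0.2 and about 49% at 0.5.

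These are scenarios, not bounds.

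**The case against.** The strongest reply is that no shortfall has been proved. Two-sided 5% is the reviewer's assumption. The aim is directional, and at one-sided 5% both the rank-sum test (85.0%) and the signed-rank test with normal differences (86%) exceed 80%. Even at two-sided 5% the gap is 2 to 4 points, or two pairs, which is far less than the spread caused by unstated assumptions about ties and shape. Enrolment of 35 leaves room for three losses before fewer than 32 pairs remain. The protocol also replaces patients who do not return their teeth (Risks, Discomforts, Potential Harms and Benefits, item 8). The number is partly a feasibility figure, and the analysis test may be set in a statistical analysis plan not seen here.

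Most of this stands, and it limits the finding. The trial is not shown to be materially underpowered, and the loss under step 4 arises only if the rank-sum test is carried into the analysis. The reply does not remove the mismatch. The paragraph names a test that does not fit the design it sizes, and it attaches a power figure to a significance level and sidedness it does not give. Those belong to the sizing statement itself and cannot be left for a later plan to supply.

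**Conclusion.** The concern holds. The test named for sizing contradicts the split-mouth design and the paragraph's own within-patient effect, and the 80% cannot be interpreted without alpha, sidedness and a tie assumption. This part depends on no assumption of the reviewer.

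The numerical part is conditional. At two-sided 5% with 30 patients, the shortfall is 3.5 points for the named test (large-sample formula) and about 2.4 points for the signed-rank test with normal, untied differences. It disappears with one-sided 5% testing (except for the sign test without ties), about 10% ties or more in a sign test, short-tailed differences, or all 35 patients analysed by the rank-sum or signed-rank test. It widens with heavy-tailed differences or a sign test without ties. This should be fixed, but it does not threaten the trial.

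**What to change.** Keep 30 evaluable and 35 enrolled. In Study Population, item 3, replace the rank-sum test with a paired test; the signed-rank test is the natural counterpart. State alpha, sidedness, that the number means patients (pairs), and the assumed share of ties and form of the differences. Then restate the power to match. If the sponsor accepts two-sided 5% and normal differences, the text could read:

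> With 30 evaluable patients (pairs) and a two-sided 5% Wilcoxon signed-rank test, power is between 77% and 78% if 70% of patients score lower on the OpalSeal tooth, assuming approximately normal differences without ties; 80% needs about 32 pairs.

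The protocol gives no scale for the WSL score, so the sponsor should confirm that this assumption is reasonable. If many ties are expected, base the statement on the sign test and report its range, from 59% without ties to about 81% with 10% ties. If a one-sided test was intended, say so and give its power.

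The cost is the wording of one paragraph. No patients are added, and the feasibility rationale is unaffected. The stated power becomes slightly less favourable unless one-sided testing or ties were intended.

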## HIPAA

1. \* Describe the protected health information that will be obtained or used in this research

The information that we would collect would include routine patient diagnostic records including radiographs, intraoral photographs as well as treatment plan

2. \* Describe the source(s) of the protected health information

We will use patient electronic health records (axiUm and Dolphin) to identify potential study participants. Access to these databases is protected by a secure username and password.

3. \* Explain how the PHI collected or used in this research is the minimum necessary to accomplish this research

There is no way to prospectively to identify eligible subjects without accessing their medical records. The PHI requested is minimum necessary to identify and recruit potential study participants.

4. \* Select all pathways this research will employ to use or access PHI

De-Identified Data (none of the 18 identifiers are recorded or associated with the research data)

Limited Data Set

Waiver of Authorization

Partial Waiver of Authorization

Signed Authorization Combined with Consent Form

Signed Authorization as Stand-Alone Form

ID: HM20011025

View: SF - Partial Waiver of Authorization

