**See the help text for additional guidance.**

The statistician will provide the study team with the computer generated random table. The study participants will be sequentially assigned a 3-digit code followed by R or L (for Right or Left) for OpalSeal. For example, patient 1 may be 001R. The key to the code will be kept by the PI in a password-protected computer and will be destroyed at the end of study.

We will have 2 codes to simplify the process and decrease confusion:

The jars handed over to the patients will have fields for date; patient initials; tooth number; Right or Left sides. Patient will be given these jars and will be instructed to hand this over to the staff at the oral surgery clinic who will place the extracted teeth in the correct containers.

Once the patient hands over the containers (with extracted teeth) to the Orthodontic Clinic, the teeth will be transferred to another jar with the original study codes. The resident and or members of the study team will collect the jars containing the teeth directly from the participant.

4. \* Will the sponsor or investigator obtain a certificate of confidentiality for this study

- No - CoC will not be Obtained
- Yes - CoC has been Obtained
- Yes - CoC Request is Pending
- Yes - Plan to Submit CoC Request

5. If the Certificate of Confidentiality has been obtained by the PI, upload it here

6. \* What will happen to the research records when the research has been completed

- Stored indefinitely with identifiers removed
- Stored indefinitely with identifiers attached
- Destroyed at the end of study once the minimum time required for data retention has been met per VCU Data Retention Policy and/or sponsor retention requirements
- Destroyed when notified by sponsor but not less than the minimum time required for data retention per VCU Data Retention Policy
- Other

7. If Other, explain

8. If "stored indefinitely with identifiers attached", explain why identifiers are necessary

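### The sample size rests on an unpaired rank-sum test although the teeth are paired within patients; the stated 80% power does not reproduce, and the WSL score behind it is not tied to a listed measurement

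*Protocol*

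**What the plan says.** In the protocol, Study Population, item 3 gives the only statistical test and the only power figure in the document. It takes 80% power, a Wilcoxon rank-sum test and a sample of 30. The effect is that "70% of subjects have lower WSL scores on the tooth with Opal Seal". It cites Noether's 1987 sample-size paper and raises recruitment to 35 for attrition. It states neither alpha nor sidedness.

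Research Description, item 4 sets the design: "we will use a split-mouth design with random assignments for interventions (OpalSeal"). Data Confidentiality and Storage, item 1 confirms that the two teeth of one patient are compared with each other.

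The same item 4 lists four laboratory tests on the extracted teeth: electron microscopy for topography, "Micro-CT to quantify the mineral density", atomic force microscopy for roughness and hardness, and fluorescence for leftover OpalSeal. None is said to yield a WSL score. HIPAA, item 1 mentions "routine patient diagnostic records including radiographs, intraoral photographs as well as treatment plan", without describing any scoring of the photographs.

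**The concern.** A rank-sum test compares two independent samples. Here each patient supplies one tooth to each arm, and the effect assumed for the power is the share of patients whose OpalSeal tooth scores better. The test named and the effect assumed therefore belong to different analyses. If the test is run as written, it judges the treatment difference against the spread between patients, which the split-mouth design was chosen to remove.

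The power figure also cannot be checked for a paired test without knowing what is measured. A coarse ordinal score can tie within a patient, whereas a continuous density almost never does. The same 70% then means different things. At stake are the main advantage of the design and the only quantitative justification for its size.

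**Working it through.** **Inputs.** Power 80%, effect 0.70 against a null of 0.50, sample of 30, recruitment of 35 (Study Population, item 3). Pairing is from Research Description, item 4. Alpha 0.05 is assumed; two-sided is the main case and one-sided is also shown.

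**1. The plan's own figure.** Noether's rank-sum formula with equal groups (c = 0.5) is N total = (z_alpha + z_beta)² / [12 c(1 − c)(p − 0.5)²].
- Two-sided: (1.960 + 0.842)² = 7.849. The denominator is 12 × 0.25 × 0.04 = 0.12. N = 65.4 in total, or 33 per group.
- One-sided: (1.645 + 0.842)² = 6.183, so N = 51.5 in total, or 26 per group.
- Two-sided power with 30 per group: Φ(√(60 × 0.12) − 1.960) = Φ(0.723) = 76.5%.
- Two-sided power with 30 in total: Φ(√(30 × 0.12) − 1.960) = Φ(−0.063) = 47.5%.
- One-sided power with 30 per group: Φ(2.683 − 1.645) = 85.0%.

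The pairing of 30 with 80% does not come out of the named test in any of these cases.

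**2. What the 0.70 means.** In the rank-sum formula, p is the chance that an OpalSeal tooth beats a control tooth drawn independently. The plan's 70% is a share of patients, each compared with himself or herself. The nearest route to 30 is Noether's signed-rank formula, n = (z_alpha + z_beta)² / [3(p′ − 0.5)²]. With normal differences, 70% above zero is a mean of 0.524 SD, so p′ = Φ(√2 × 0.524) = 0.771. Then n = 36 pairs two-sided and 29 one-sided. That is neither the named test nor a stated assumption.

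**3. Cost of ignoring the pairing.** Take 30 pairs, normal data, and 70% of patients favouring OpalSeal throughout. With correlation ρ, the shift in units of between-patient SD is 0.524 × √(2(1 − ρ)).

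| ρ | shift (between-patient SD) | rank-sum power (simulated) | signed-rank power (simulated) |
|---|---|---|---|
| 0.3 | 0.62 | about 66% | 77-78% |
| 0.5 | 0.52 | about 50% | 77-78% |
| 0.7 | 0.41 | about 23% | 77-78% |

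The documents give no correlation; these values are an assumed range.

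**4. Dependence of paired power on the outcome.** Two-sided 0.05, 70% lower on OpalSeal in every row:

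| Paired reading | 30 pairs | 35 pairs |
|---|---|---|
| Exact sign test, 70/30, no ties (reject at 21 or more of 30, 24 or more of 35, or the mirror image) | 59% | 65% |
| Paired t-test, normal differences, mean 0.524 SD | 79% | 85% |
| Exact sign test, 70% lower, 10% tied, 20% higher, ties dropped | 81% | 87% |

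The 70/10/20 split is an assumption; the protocol gives no tie rate.

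**5. Tracing the score.** The procedures are bonding, enamel reduction, tooth collection, a survey and the four laboratory tests. The survey gathers patient factors. The fluorescence test measures remaining primer. Micro-CT density could stand for lesion severity, but the protocol does not say so, and its direction is the reverse: lower is better for the score, higher is better for density.

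**The case against.** The best defence is that 30 patients are about right. Under normal differences, 70% favouring OpalSeal gives a paired t-test 79% power with 30 pairs and 85% with 35, and simulation gives the signed-rank test about 77% and 84%. This stands. A reader might infer from the 59% row that the trial is badly underpowered. The documents do not support that: no sign test is planned, and it discards the size of each difference.

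A reader might also infer that no WSL score exists. That goes too far. The form has slots for uploaded data-collection forms and instruments that are not shown, and one of them could hold a scale. Elsewhere the protocol describes white spots as early caries and speaks of reducing demineralization, so mineral density is not a remote stand-in. What remains is that the visible text names a score and connects it to nothing.

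Nor do the two research questions compete for the power figure. The question "Can OpalSeal offer protection against decay on the sides of teeth following IPR" is separate from the WSL question, and the sample-size text already places its figure with WSL around the brackets.

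Finally, an analysis plan that is not shown may specify a paired test. The protocol would still state an unpaired one as the basis for its size.

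**Conclusion.** The point holds as a mismatch inside the protocol: an independent-groups test for paired teeth, supported by a power figure that does not reproduce for that test. At two-sided 0.05 the shortfall on the plan's own terms is small (76.5% against 80%) if 30 means 30 teeth per arm. The larger cost comes from running the rank-sum test on correlated teeth, with power falling to about 50% at a correlation of 0.5. With positive correlation the error is conservative: it loses power and does not inflate false positives.

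The unlinked WSL score is the lesser part, closer to missing detail than to error. It matters because the paired power with 30 patients runs from 59% to 81% depending on test and ties. The conclusion rests on assumed alpha, sidedness, correlations, normality and tie rate, none of which the protocol states. It does not show that 30 or 35 patients are too few.

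**What to change.** In Study Population, item 3:
- Replace the rank-sum test with a within-patient paired test, for example Wilcoxon signed-rank.
- State which measurement is the WSL outcome. It can be a read-out already listed, such as micro-CT mineral density (where higher favours OpalSeal), or a score cited from the form that holds it.
- Restate the power for that paired test, with alpha, sidedness and the assumed distribution of differences or tie rate. Keep the sample size.

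Whichever outcome is chosen, read it under codes that hide treatment and OpalSeal side. As written, the code in Data Confidentiality and Storage, item 1 includes "whether the tooth received OpalSeal (e) or Transbond XT (c"), and item 3 has patients "sequentially assigned a 3-digit code followed by R or L (for Right or Left) for OpalSeal". Choosing a micro-CT region is open to the same influence as grading a lesion, so this applies to both options.

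The cost is protocol wording plus relabelling of specimens before reading. The restated power may be slightly less favourable than 80%, and the other read-outs become secondary for the bracket question.
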